## 8.3 Analyses Plans

### 8.3.1 Analysis Population

We will conduct an intention-to-treat analysis of efficacy. All randomized patients will be evaluated.

For evaluation of safety, we will restrict the arm-specific samples to all patients who have received at least one dose of investigational therapy.

### 8.3.2 Primary Analysis (or Analysis of Primary Endpoints)

#### Primary Endpoint 1 Analysis (Evaluation of Efficacy)

For each arm objective response rate (ORR) will be defined as the proportion of participants randomized to that arm whose status is SD or better (CR, PR) at 24 weeks' follow-up. Within each treatment arm, the observed ORR will be compared to the respective null (ineffective) rate using the decision rule provided by the Simon's two-stage design. In addition to calculating the ORR, we will calculate the corresponding one-sided 95% confidence interval by appropriately accounting for the Simon's two-stage design: given the observed response number ( $s$ ), testing of the null hypothesis of  $H_0: p \leq p_0$  will reject the null if the probability of observing as many or less than the observed number of responses ( $s$ ) is less than the significance level:  $\text{Prob}(S \leq s | p_0) < \alpha$ . Using this hypothesis inversely, we can construct a  $(1-\alpha)100\%$  one-sided confidence interval is given as a set

$$\{p: \text{Prob}(S \leq s | p_0 = p) < \alpha\}$$

where  $\text{Prob}(S \leq s \mid p_0 = p)$  indicates the joint distribution of stage to stop and observed response number ( $s$ ) as in Chang et al., 1989. Similarly, the observed rates will be compared between the treatment arms using the Z-test and appropriately accounting for the Simon's two-stage design.

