### 3.2 Sample Size

We adopt a randomized two-arm trial with futility early stopping built-in within each treatment arm using a Simon's two-stage design (Simon, 1989). The effect of vorinostat on pembrolizumab and the effect of pembrolizumab and tamoxifen in this biomarker-selected population of ER+ breast cancer patients will be first tested against the respectively chosen null rate in the first stage within the treatment arms and then compared between the treatment arms.

65 patients to be treated under the study/enrolled in the investigational portion of the study (sample size for primary objective).

**For Arm A (vorinostat + TAM + pembro):** The null hypothesis that the true response rate for pembrolizumab and vorinostat in ER+ pretreated patients alone without biomarker enrichment is 0.15 which will be tested against the alternative that response rate of pembrolizumab in a biomarker select population is 0.40. In the first stage, 13 patients will be accrued. If there are 2 or fewer responses in these 13 patients, the study will be stopped. Otherwise, 22 additional patients will be accrued for a total of 35. The null hypothesis will be rejected if 10 or more responses are observed in 35 patients. This design yields a type I error rate of 0.025 and power of 0.9 in this treatment arm when the true response rate is 0.4 in this patient subpopulation.

**For Arm B (pembro + TAM):** The null hypothesis that the true response rate for pembrolizumab in ER+ pretreated patients alone is 0.10 which will be tested against the alternative that response rate of pembrolizumab in a biomarker select population is 0.35. In the first stage, 11 patients will be accrued. If there are 1 or fewer responses in these 11 patients, the study will be stopped. Otherwise, 19 additional patients will be accrued for a total of 30. The null hypothesis will be rejected if 7 or more responses are observed in 30 patients. This design yields a type I error rate of 0.025 and power of 0.9 in this treatment arm when the true response rate of pembro + TAM treatment is 0.35 in this patient subpopulation.

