### 8.1 Sample Size Considerations

#### 8.1.1 Sample Size and Power Estimate

For Arm A (pembro + vorinostat + TAM): The null hypothesis that the true response rate for pembrolizumab and vorinostat in ER+ pretreated patients alone without biomarker enrichment is 0.15 which will be tested against the alternative that response rate of pembrolizumab in a biomarker select population is 0.40. In the first stage, 13 patients will be accrued. If there are 2 or fewer responses in these 13 patients, the study will be stopped. Otherwise, 22 additional patients will be accrued for a total of 35. The null hypothesis will be rejected if 10 or more responses are observed in 35 patients. This design yields a type I error rate of 0.025 and power of 0.9 in this treatment arm when the true response rate is 0.4 in this patient subpopulation.

For Arm B (pembro + TAM): The null hypothesis that the true response rate for pembrolizumab in ER+ pretreated patients alone is 0.10 which will be tested against the alternative that response rate of pembrolizumab in a biomarker select population is 0.35. In the first stage, 11 patients will be accrued. If there are 1 or fewer responses in these 11 patients, the study will be stopped. Otherwise, 19 additional patients will be accrued for a total of 30. The null hypothesis will be rejected if 7 or more responses are observed in 30 patients. This design yields a type I error rate of 0.025 and power of 0.9 in this treatment arm when the true response rate of pembro and TAM treatment is 0.35 in this patient subpopulation.

Based on earlier results in Section 1.3 and hypothesized treatment effects, we will most likely to enroll 46 evaluable patients (~65% chance), whereas the possible enrollment ranges from 24 to 65. For the comparison of the treatment arms, the proposed design will have 72.53% power for the Fisher's exact test at 0.1 significance level when the true response rates are 0.4 and 0.1 for the immune priming and the no immune priming treatment arm.

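### The one-sided 95% confidence interval for each arm's response rate is defined with the wrong tail and the wrong inequality, so as printed it covers the true rate at most 5% of the time

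*Combined protocol and SAP*

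**What the plan says.** Section 8.3.2 gives three instructions for each arm's response rate.

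- **Test.** The observed rate is compared with its null value "using the decision rule provided by the Simon's two-stage design". Sections 3.2 and 8.1.1 state that rule. For Arm A: "The null hypothesis will be rejected if 10 or more responses are observed in 35 patients". For Arm B: "The null hypothesis will be rejected if 7 or more responses are observed in 30 patients".
- **Interval.** In addition, "we will calculate the corresponding one-sided 95% confidence interval by appropriately accounting for the Simon's two-stage design".
- **Construction of the interval.** The section sets up H0: p ≤ p0 and says the test "will reject the null if the probability of observing as many or less than the observed number of responses" falls below the significance level. In symbols, it rejects if Prob(S ≤ s | p0) < α. It then defines the (1 − α)100% interval as {p : Prob(S ≤ s | p) < α}, using the joint distribution of stopping stage and response count.

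**The concern.** The construction has two separate errors.

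1. **Tail.** Under H0: p ≤ p0, a large S is the evidence against the null. The p-value is Prob(S ≥ s | p0). The section uses the lower tail, in words and in symbols.
2. **Inequality.** A confidence set obtained by inverting a test keeps the values of p that the test does not reject. The printed set keeps the values with tail probability below α, which are the rejected ones.

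The rejection sentence also contradicts the Simon rule cited in the same paragraph, which rejects for many responses.

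At stake is the precision reported for the primary endpoint in each arm. An interval programmed from the text would lie wholly above the observed rate for every outcome short of all patients responding, and so would suggest a higher response rate than the data support.

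**Working it through.** **Inputs (Sections 3.2 and 8.1.1; interval level from 8.3.2)**

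| | Arm A | Arm B |
|---|---|---|
| Stage 1 | 13 patients, stop if ≤ 2 | 11 patients, stop if ≤ 1 |
| Total | 35 | 30 |
| Reject H0 | ≥ 10 | ≥ 7 |
| Null / alternative rate | 0.15 / 0.40 | 0.10 / 0.35 |
| Interval level | one-sided 95%, α = 0.05 | same |

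**Distribution of S.** With stage sizes n1 and n2 and stopping boundary r1:

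- for s ≤ r1, Prob(S = s) = C(n1, s) p^s (1−p)^(n1−s);
- for s > r1, Prob(S = s) is the sum over x > r1 of the stage 1 probability of x times the stage 2 probability of s − x.

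The only early stop is for futility, so S determines the stage at which the arm stopped, and ordering outcomes by S is unambiguous.

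**Step 1: reproduce the design.** Prob(S ≥ 10 | 0.15) = 0.0249 and Prob(S ≥ 10 | 0.40) = 0.904 in Arm A. Prob(S ≥ 7 | 0.10) = 0.0220 and Prob(S ≥ 7 | 0.35) = 0.900 in Arm B. These agree with the stated 0.025 and 0.9, so the count rules are sound and use the upper tail.

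**Step 2: the printed rejection sentence.** Prob(S ≤ s | p0) is smallest at s = 0. That is 0.85^13 = 0.121 in Arm A and 0.90^11 = 0.314 in Arm B. Both exceed 0.05, so the sentence could never reject, whatever the data. At the actual cut-offs the printed tail is Prob(S ≤ 10 | 0.15) = 0.990 and Prob(S ≤ 7 | 0.10) = 0.993.

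**Step 3: the printed interval against the corrected one.** The edge of the printed set solves Prob(S ≤ s | p) = 0.05. The corrected lower bound solves Prob(S ≥ s | p) = 0.05.

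| Outcome | Observed rate | Printed set | Corrected 95% interval |
|---|---|---|---|
| Arm A, 10/35 | 0.286 | p > 0.454 | [0.168, 1] |
| Arm A, 14/35 | 0.400 | p > 0.554 | [0.261, 1] |
| Arm B, 7/30 | 0.233 | p > 0.413 | [0.119, 1] |
| Arm B, 10/30 | 0.333 | p > 0.502 | [0.194, 1] |

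Each printed set excludes its own point estimate.

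**Step 4: coverage.** Coverage at a true rate p is the sum of Prob(S = s | p) over every s whose set contains p.

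- Arm A, p = 0.40: Prob(S ≤ 1) = 0.6^13 + 13 × 0.4 × 0.6^12 = 0.0013 + 0.0113 = 0.0126. Prob(S ≤ 2) adds 78 × 0.4² × 0.6^11 = 0.0453 and passes 0.05. The printed set therefore contains 0.40 only when s is 0 or 1, and coverage is 0.013.
- Arm B, p = 0.35: Prob(S = 0) = 0.65^11 = 0.0088. Prob(S ≤ 1) adds 11 × 0.35 × 0.65^10 = 0.0518 and passes 0.05. Coverage is 0.009.
- At each null rate no s qualifies (step 2), so coverage is 0.
- Over true rates from 0.005 to 0.995, coverage never exceeds 0.050 in either arm. This is general: with F the distribution function of S, Prob(F(S) < α) ≤ α always.

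**Step 5: what each error does.**

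| Correction | Coverage, both arms | Type of bound |
|---|---|---|
| None (as printed) | at most 0.05 | lower edge above the estimate |
| Tail only | at most 0.05 | rejected values still kept |
| Inequality only | at least 0.95 | upper bound, does not match H0: p ≤ p0 |
| Both | at least 0.95 | lower bound, matches the test |

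**Step 6: agreement of the corrected bound with the cut-offs.** In Arm A the 95% lower bound is 0.148 at s = 9 (does not exclude 0.15) and 0.168 at s = 10 (excludes it). In Arm B it is 0.097 at s = 6 (does not exclude 0.10) and 0.119 at s = 7 (excludes it).

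**The case against.** The strongest reply is that the intent can be recovered. The section announces a confidence interval obtained by inverting a test. The printed set excludes its own estimate, so an analyst would see the fault in the first output. The governing test is the Simon rule, which is correct, and the response rate itself is calculated correctly. This limits the harm, and it is why the point does not touch the trial's decisions. It does not make the formula right. An analyst who noticed would still have to choose the direction of the bound after seeing data.

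A second reply is that the coverage failure comes from the inequality alone, a single printed character. With that character changed and the lower tail kept, the result is a valid 95% upper bound. This is true, but the same sign appears in the rejection sentence, so a slip in the set alone is unlikely. The tail error is also spelled out in words and stands regardless. The section does not name a lower or an upper bound; a lower bound is inferred from H0: p ≤ p0.

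A third reply is that the 95% level does not match the 0.025 design level, so the agreement in step 6 comes from discreteness. This stands as a qualification. Prob(S ≥ 9 | 0.15) = 0.0545 and Prob(S ≥ 6 | 0.10) = 0.0570 are only just above 0.05. If Arm A ended with 34 patients, 9 responses would give a bound of 0.151, above 0.15 although the cut-off of 10 is not met. With 28 in Arm B, 6 responses would give 0.103, above 0.10 although the cut-off of 7 is not met.

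**Conclusion.** The concern holds. As printed, the interval has the wrong tail for its stated null hypothesis and keeps the rejected values. Its coverage is at most 0.050 against a nominal 0.95. At the cut-offs it begins at 0.454 instead of 0.168 (Arm A) and at 0.413 instead of 0.119 (Arm B).

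These figures assume the stated stage sizes and boundaries, outcomes ordered by response count, and interval α = 0.05. At α = 0.025 the printed coverage is at most 0.025, so the conclusion does not depend on the level.

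The error is confined to the interval and the rejection sentence that introduces it. Sample size, cut-offs, type I error, power, futility stopping and the go/no-go decision do not change. It should be fixed before analysis because it concerns the precision reported for the primary endpoint.

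**What to change.** Rewrite the interval text in Section 8.3.2 to say:

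1. The within-arm test follows the Simon count rules of Section 8.1.1, and these govern the decision.
2. The test to be inverted rejects H0: p ≤ p0 if Prob(S ≥ s | p0) ≤ α.
3. The reported interval is [pL, 1], where pL is the lower bound of {p : Prob(S ≥ s | p) > α}, computed from the two-stage distribution already cited.
4. The interval uses α = 0.05, stated explicitly because the arm tests are designed at 0.025.

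The 95% level can stay: at the planned 35 and 30 patients the corrected bound excludes the null rate exactly when the cut-off is met. Because this can fail if an arm ends short, point 1 should add that the interval is descriptive and does not override the count rule.

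The cost is the wording of one paragraph. Sample size, cut-offs, error rates and confidence level are unchanged.

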### 8.3.3 Secondary Analysis (or Analysis of Secondary Endpoints)

We will use median (DOR, OS, PFS, computed by the Kaplan-Meier estimator) and percentages (% irRC) to summarize secondary endpoints. The respective confidence intervals will be computed as well.

### 8.3.4 Exploratory/Correlative Analysis/Assessments

#### 8.3.4.1 Analysis of Tissue-based Endpoints

*Note:* Tissue will be used for multiple different exploratory assays. In the event that there is insufficient tissue to perform all assays for an individual subject, the tissue should be prioritized for assays as follows, in which the first assay described is the highest priority.

##### Tumor PD-L1 Assessment

PD-L1 protein expression on tumor tissue from pre-treatment and post-Cycle-3 biopsies and any other tumor biospecimens obtained will be evaluated immunohistochemically and scored on a scale of 0, 1, 2, or 3. This scoring will be used for the determination of relationships between tumor PD-L1 expression and clinical responses described above. Specifically, in addition to hypothesizing that delayed pembrolizumab treatment (i.e., Arm A) will increase tumor response, we hypothesize that (i) PD-L1 expression will stimulate tumor response, (ii) but will not be associated with treatment (because PD-L1 is stimulated by vorinostat, not pembrolizumab).

For analysis, PD-L1 expression level, scored as  $\{0, 1, 2, 3\}$ , will be classified as binary (0 = negative; 1-3 = positive); across two time-points, this defines four types of PD-L1 participants:  $\{0, 0; 0, 1; 1, 0; 1, 1\}$ . We will use logistic regression to estimate Cycle-6 tumor response rate (95% CI) as a function of study arm and PD-L1 level at baseline and Cycle 3. Either time-point will be eliminated from the model if its effect is weak ( $p > 0.2$ ), leaving two types of PD-L1 participants: either  $\{0, 0; 1, 1\}$  or  $\{0, 0; 0, 1\}$ .

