### **1.3.1.1 Programmed cell death 1 (PD-1) and its ligand PD-L1 in breast cancer**

Inhibition of the PD-L1/PD-1 axis has been a major milestone in many cancer types. Clinically, epigenetic immune regulation has been implicated in priming lung cancer cells to PD-1 inhibitors, which resulted in prolonged responses. Increased PD-L1 expression has been observed in hormone therapy resistance, frequently reported with loss of progesterone receptor (PR) expression, a measure of hormone therapy resistance. Hence, PD-1 inhibitors may have a role in hormone therapy-resistant breast cancer, and PD-1 inhibitors may be more effective after epigenetic immune priming. Several investigators have shown that HDAC inhibitors have immune modulatory functions, including modulation of Tregs, FoxP3 expression, changes in tumor-infiltrating lymphocytes (TILs), induction of PD-L1 expression, and blockage of PD-1 signaling. Hence, the combination of HDAC inhibitors may potentiate the efficacy of PD-1 inhibitors.

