## 3 Study Design

### 3.1 Characteristics

We propose a single site Phase II, two-arm, open-label unblinded, 65-patient trial in patients with hormone therapy-resistant breast cancer (HTR) to test the role of epigenetic priming in a biomarker enriched patient population in HTR breast cancer. The two arms include Arm A: pembrolizumab, vorinostat, and tamoxifen and Arm B pembrolizumab and tamoxifen.

Patients will be evaluated for response at 9 weeks ( $\pm 1$  week) by RECIST1.1 (using IR-RECIST) and will continue on therapy if they have stable disease or response at the time of disease evaluations. Patients with progression on imaging but are clinically stable, may stay on study but will require follow-up staging after 4-6 weeks. Patients will be assessed continually for safety and tolerability as well as for any adverse events. If progression on therapy with pembrolizumab, patient may continue if clinically indicated and be re-evaluated after 4-8 weeks.

We will follow AEs of clinical interest as defined by Merck and will dose modify pembrolizumab as per Merck guidelines. We have significant prior experience with vorinostat, tamoxifen, and pembrolizumab combination and are facile with managing drug toxicities.

Tissue biopsies of all patients will be collected prior to enrollment to assess for pre-treatment of our immune signature and PD-L-1 expression. Follow up biopsies and peripheral blood collection will be taken from all patients post-treatment at 8-10 weeks to characterize changes in local tissue effects and antigen-specific cellular and humoral immune responses in peripheral blood.

Patients will be stratified by prior number of hormonal and chemotherapies.

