## 6.1 Study Calendar

Period/ Procedure	Pre- Screening	Screening 	Cycle 1			Cycle 2	Future Cycles 	Restaging or Off-Study Visit Survival Follow-up
Study Day/Visit Day*	-365 to -28	-28 (±3)	1 (±3)	10-12 (±3)	15 (±3)	1 (±3)	1 (±3)	9 weeks Post Start of Tx (±7)
Study Treatment/Drug Administration								
Pembrolizumab			200 mg q every 3 weeks; start on C1D1					
Vorinostat			400 mg once a day, 4 days on, 3 days off, weekly every cycle					
Tamoxifen			20 mg once a day continuously					
Administrative Procedures								
Prescreening ICF	X							
Informed consent		X						
Clinical Assessments								
Physical exam		X	X		X	X	X	
Vital signs		X	X		X	X	X	
Performance status		X	X		X	X	X	
Medical history		X						
Concomitant medications		X	X		X	X	X	
Toxicity Assessment 		X	X		X	X	X	X 
Drug Diaries 			X			X	X	
Documentation of Response		X					X	

 All screening procedures must be performed within 28 days unless otherwise indicated. Pre-study tests, History and Physical may be used for Day 1 tests if within 2 weeks

 Cycle delays up to 14 days for non-medical reason (e.g. holidays) are acceptable without notification of regulatory agencies

 Therapy delay for palliative radiation should be based on discussion with the study sponsor and the treating physician, every effort should be made not to hold therapy, patients, where vorinostat is being held for more than 4 weeks, may stay on study if there is felt to be a benefit

 Toxicity assessment must be performed until all treatment-related toxicities have been resolved or decreased to grade 1. Adverse events must be recorded up to 30 days after termination on study

 Drug diaries will be administered for vorinostat and tamoxifen (oral drugs) only on the first day of every cycle

Period/ Procedure	Pre- Screening	Screening 	Cycle 1			Cycle 2	Future Cycles 	Restaging or Off-Study Visit Survival Follow-up
Study Day/Visit Day*	-365 to -28	-28 (±3)	1 (±3)	10-12 (±3)	15 (±3)	1 (±3)	1 (±3)	9 weeks Post Start of Tx (±7)
Laboratory Assessments								
Hematology 		X	X		X	X	X	
Comprehensive Metabolic Panel 		X	X		X	X	X	
Thyroid Function 		X				X	X (odd cycles)	
Tumor Markers 		X	X			X	X	
Pregnancy test 		X					X	

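### The PD-L1 hypotheses belong to the earlier trial design, and in this trial the arm term adjusted for Cycle-3 PD-L1 is not the total vorinostat effect (exploratory, low severity)

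*Combined protocol and SAP*

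**What the plan says.** **The model.** Section 8.3.4.1, Tumor PD-L1 Assessment, scores PD-L1 as negative or positive before treatment and after Cycle 3. One logistic regression then estimates Cycle-6 tumor response "as a function of study arm and PD-L1 level at baseline and Cycle 3". A PD-L1 time-point is dropped if its p-value exceeds 0.2.

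**The hypotheses.** The section expects that "delayed pembrolizumab treatment (i.e., Arm A) will increase tumor response". It adds that (i) "PD-L1 expression will stimulate tumor response" and that (ii) PD-L1 will be unrelated to treatment, "because PD-L1 is stimulated by vorinostat, not pembrolizumab".

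**The design.** Section 3.1 states: "The two arms include Arm A: pembrolizumab, vorinostat, and tamoxifen and Arm B pembrolizumab and tamoxifen". For pembrolizumab the Study Calendar (6.1) gives "200 mg q every 3 weeks; start on C1D1", and Tables 5.2 and 5.3 give the same pembrolizumab schedule in both arms. The second biopsy is due at the end of Cycle 3, preferably while the patient is on vorinostat (6.1, footnote 11).

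**The earlier study.** Section 1.5 describes pembrolizumab given at once or after three weeks of priming. Section 1.3.1.2 says that all patients in that study received vorinostat.

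**The concern.** The hypotheses and the model appear to come from a trial in which both arms received vorinostat and differed in when pembrolizumab began. There, PD-L1 need not differ by arm, and Cycle-3 PD-L1 could pass as a harmless covariate. Here vorinostat is what separates the arms. The reason given for hypothesis (ii) now predicts the opposite of that hypothesis, and Cycle-3 PD-L1 becomes a post-treatment variable on a possible path from arm to response.

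What is at stake is how the arm term is read. The section states a hypothesis about the effect of arm and puts arm in the model. If the fitted coefficient is taken as the vorinostat effect, any part that works through PD-L1 has been removed from it. Section 8.3 also names no comparison of Cycle-3 PD-L1 between arms, so the PD-L1 part of exploratory objective 6 (section 2.4) has no matching method.

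**Working it through.** **Step 1. The premises.**

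- Arm to PD-L1: the section says that vorinostat stimulates PD-L1. Section 1.3.1.1 likewise lists "induction of PD-L1 expression" among the effects of HDAC inhibitors. Only Arm A receives vorinostat.
- PD-L1 to response: this is hypothesis (i).
- Together these make Cycle-3 PD-L1 a mediator of the arm effect, and they contradict hypothesis (ii).

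**Step 2. Inputs for the size.** The plan gives no effect size, power or sample size for this model, so there is no figure to reproduce.

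- From section 8.1.1: response 0.40 in Arm A and 0.10 in Arm B. They were set for the between-arm comparison of the primary endpoint and are borrowed here for Cycle-6 response.
- Assumed, because the documents give no values: Cycle-3 PD-L1 positivity m_B and m_A, and a PD-L1/response odds ratio of 2, 4 or 8.

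**Step 3. Total effect.** The risk difference is 0.40 − 0.10 = 0.30. The odds ratio is (0.40/0.60)/(0.10/0.90) = 6.00.

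**Step 4. Adjusted effect.** Let logit P(response) = a + b·arm + c·PD-L1, with c the log of the PD-L1 odds ratio. Solve for a and b so that the arms average 0.10 and 0.40. The adjusted odds ratio is exp(b). The adjusted risk difference averages the two PD-L1 strata over the pooled positivity (m_B + m_A)/2.

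One case in full, with m_B = 0.20, m_A = 0.50 and PD-L1 odds ratio 4:

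- Arm B response is 0.0683 if PD-L1 negative and 0.2268 if positive: 0.8×0.0683 + 0.2×0.2268 = 0.100.
- Arm A response is 0.2408 if negative and 0.5592 if positive: 0.5×0.2408 + 0.5×0.5592 = 0.400.
- Pooled positivity is 0.35, so the adjusted risk difference is 0.65×(0.2408 − 0.0683) + 0.35×(0.5592 − 0.2268) = 0.228.

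| PD-L1 positive, Arm B vs A | Adjusted arm OR (PD-L1 OR 2 / 4 / 8) | Adjusted risk difference (2 / 4 / 8) |
|---|---|---|
| 10% vs 30% | 5.28 / 4.82 / 4.62 | 0.275 / 0.249 / 0.222 |
| 20% vs 50% | 4.98 / 4.33 / 3.95 | 0.265 / 0.228 / 0.195 |
| 20% vs 70% | 4.33 / 3.26 / 2.55 | 0.242 / 0.186 / 0.138 |
| 30% vs 30% (control) | 6.21 / 6.97 / 8.60 | 0.300 / 0.300 / 0.300 |

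In the control row arm does not change PD-L1. The risk difference stays at 0.300, and the odds ratio moves only through non-collapsibility. The loss in the other rows therefore arises because arm changes PD-L1.

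**Step 5. Is the term at least a clean direct effect?** Not without a further assumption. In a simulation of 400,000 patients, arm had no effect on response, vorinostat raised PD-L1 positivity from 24% to 50%, and one unmeasured factor influenced both PD-L1 and response. The arm odds ratio was 1.00 unadjusted and 0.70 adjusted for PD-L1.

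**Step 6. The p>0.2 rule.** The model with arm and Cycle-3 PD-L1 was simulated 1,500 times per setting at 20% vs 50% positivity; runs without a usable fit were dropped, leaving 1,414 to 1,483. The 35/11 split is the enrollment of 46 that the plan calls most likely: (1 − 0.0579)×0.6974 = 0.657, matching its figure of about 65%.

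| Patients, Arm A/B | Cycle-3 term kept, PD-L1 OR 2 | Cycle-3 term kept, PD-L1 OR 4 |
|---|---|---|
| 35/30 | 46% | 83% |
| 35/11 | 42% | 78% |

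Whether the reported arm term is adjusted for Cycle-3 PD-L1 would thus vary from one realization of the trial to another.

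**The case against.** **The model serves another aim.** The section says that the scores are for relating PD-L1 to clinical response. For that aim arm belongs in the model: if vorinostat affects both PD-L1 and response, leaving arm out would confound the association. The section never says that the arm coefficient will be read as the total effect. This stands, and it is why the model should be kept for that purpose. It does not rescue the hypotheses, and the section does state one about arm.

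**The total effect is tested elsewhere.** Section 8.3.2 compares the arms by a Z-test without PD-L1, and section 8.3.1 specifies intention to treat. A vorinostat effect acting through PD-L1 would still appear there. A shrinkage from that result to the adjusted one could even point towards mediation, subject to unmeasured common causes. This stands.

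**A reader might infer that the model would hide priming, with the arm effect vanishing.** That can be constructed. Suppose PD-L1 positivity is 70% vs 30% and response is 40% if positive and 10% if negative in both arms. The totals are 0.7×0.4 + 0.3×0.1 = 0.31 and 0.3×0.4 + 0.7×0.1 = 0.19, a 12-point difference, while the adjusted arm effect is zero. But zero was built in by assuming that the whole effect passes through PD-L1. The documents give no such figures. The pilot in section 1.3.1.2 had low PD-L1 expression, and it linked benefit to exhausted CD8 cells and to Treg reduction. Attenuation is supported; disappearance is not.

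**The elimination rule sometimes removes the Cycle-3 term.** It does, and the over-adjustment then goes with it. But chance should not decide which effect is reported.

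**Conclusion.** Hypothesis (ii) and the description of Arm A are wrong as written for this trial. That rests on the text alone.

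When Cycle-3 PD-L1 is in the model, the arm term does not estimate the total vorinostat effect. Given the section's own premises, it is attenuated to the extent that vorinostat acts through PD-L1: from a risk difference of 0.30 to 0.275–0.138, or from an odds ratio of 6.00 to 5.28–2.55. These sizes depend on assumed PD-L1 rates and PD-L1/response odds ratios. There is no attenuation if vorinostat does not change PD-L1, or if PD-L1 is unrelated to response and shares no unmeasured cause with it. To call the term biased is correct only relative to the total effect.

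Severity is low. The model is exploratory, and no primary or secondary conclusion, sample size or stopping rule depends on it.

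**What to change.** In section 8.3.4.1, Tumor PD-L1 Assessment:

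1. Rewrite the hypotheses for vorinostat versus no vorinostat. Remove the reference to delayed pembrolizumab, and state that Cycle-3 PD-L1 is expected to differ by arm.
2. Where this section estimates the arm effect, adjust for baseline PD-L1 only and keep that term whatever its p-value. A standardized risk difference avoids the non-collapsibility shift seen in the control row.
3. Compare Cycle-3 PD-L1, or its change from baseline, between arms as an outcome. This gives the PD-L1 part of exploratory objective 6 a method.
4. Keep the model with arm and Cycle-3 PD-L1 only for the PD-L1/response association, and state that its arm term is not the total treatment effect.
5. Delete the p>0.2 elimination rule.

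The cost is analysis-plan wording. No additional data, biopsies or patients are needed.
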